## PROTOCOL AMENDMENT SUMMARY OF CHANGES

## Protocol Amendment 7 (Approval date 07 July 2022)

#### **Overall Rationale for the Amendment:**

The protocol was amended to permit the shipping of investigational product and/or ancillary supplies from the study site to a subject's home or other designated location in situations other than COVID-19-related disruptions to study conduct. Additional revisions were made to align the endpoints and analyses with the Statistical Analysis Plan and to align study procedures with current company practices.

Minor formatting and stylistic revisions were made to align with current templates, and any identified typographical errors were corrected; these are not identified individually in the descriptions below.

Description of change	Section(s) affected	Rationale for Change
Adding the option to ship investigational product and/or ancillary supplies from the study site to a subject's home or other designated location in situations other than COVID-19-related disruptions to study conduct.	Section 12.3.4, Section A1.1.5.4	Align with current company practice permitting direct-to-subject shipments, where permitted.
Remove measurement of C3Nef after Part A of the study.	Synopsis, Section 9.2.3, Section 16.2.2.3, Table A1, Table A3	Recommended to remove C3NF testing post-dose as pegcetacoplan interferes with the assay performance. Testing in Part A is already completed and reported so is retained.
Add CH50 to the list of pharmacodynamic assays.	Synopsis, Section 9.2.5, Section 14.3	Previously omitted from list of complement assays to be evaluated.
Updated description of the analyses of pharmacokinetic parameters.	Synopsis	Align with description in Section 16.2.4.
Updated procedures for reporting SAEs.	Section 15.2	Align with current company practices.
Update procedures for reporting changes in severity of AEs.	Section 15.2.2	Align with current company practices.
Updated procedures for reporting pregnancies.	Section 15.3	Align with current company practices.
Updated definition of TEAEs to include events up to 8 weeks after the last dose of study medication.	Section 16.2.3.1	Align with current understanding of pegcetacoplan pharmacology and with company reporting practices.
Reduce frequency of collection of ADA samples in the long-term extension portion of the study to approximately every 24 weeks.	Table A1, Table A3	Minimize unnecessary blood collections; reduced frequency should be sufficient to effectively monitor immunogenic responses.
Add recommendations regarding vaccination against COVID-19.	Section A2.1.5	Align with current company practices.

Abbreviations: ADA = antidrug antibody; AE = adverse event; C3Nef = C3 nephritic factor; CH50 = total hemolytic complement activity assay; COVID-19 = coronavirus disease 2019; SAE = serious adverse event.

07 July 2022

# 2. ABBREVIATIONS

Abbreviation	Definition
ACIP	Advisory Committee on Immunization Practices
ACR	albumin-to-creatinine ratio
ADA	antidrug antibody
AE	adverse event
AH50	complement alternative pathway assay
ALT	alanine aminotransferase
aPTT	activated partial thromboplastin time
AST	aspartate aminotransferase
AUC	area under the serum concentration versus time curve
$\mathrm{AUC}_{0\text{-}\infty}$	area under the serum concentration versus time curve, from time 0 to infinity
AUC tau	area under the serum concentration versus time curve, over the dosing interval
β-HCG	beta human chorionic gonadotropin
C3G	C3 glomerulopathy
C3GN	C3 glomerulonephritis
C3NeF	C3 nephritic factor
CH50	total hemolytic complement activity assay
C max	maximum observed serum concentration
CKD/EPI	Chronic Kidney Disease Epidemiology Collaboration
CL	clearance
CL/F	apparent total body clearance after extravascular administration
CRF	case report form
DDD	dense deposit disease
ECG	electrocardiogram
eCRF	electronic case report form
eGFR	estimated glomerular filtration rate
ESRD	end-stage renal disease
Gd-IgA1	galactose-deficient IgA
GGT	gamma-glutamyl transferase
GLP	Good Laboratory Practice
GMP	Good Manufacturing Practice
Hb	hemoglobin
HBsAg	hepatitis B surface antigen
HCV	hepatitis C

Abbreviation	Definition
hERG	human ether-à-go-go-related gene
HIV	human immunodeficiency virus
IB	investigator's brochure
ICH	International Council for Harmonisation of Technical Requirements for Pharmaceuticals for Human Use
IEC	independent ethics committee
IgAN	immunoglobulin A nephropathy
IND	investigative new drug
INR	international normalized ratio (for coagulation)
IRB	institutional review board
ITT	intent-to-treat
IV	intravenous
LDH	lactate dehydrogenase
LN	lupus nephritis
MBL	mannose-binding lectin
MedDRA	Medical Dictionary for Regulatory Activities
NOAEL	no-observed-adverse-effect level
NOEL	no observed effect level
PCR	protein-to-creatinine ratio
PD	pharmacodynamic(s)
PI	primary investigator
PLA2R	phospholipase A2 receptors
PK	pharmacokinetic(s)
PNH	paroxysmal nocturnal hemoglobinuria
primary MN	primary membranous nephropathy
RBC	red blood cell
SAP	statistical analysis plan
SC	subcutaneous
t 1/2	terminal elimination half-life
T max	time at which maximum serum concentration is observed
ULN	upper limit of normal
uPCR	urine protein-to-creatinine ratio
V z /F	apparent volume of distribution after extravascular administration
WBC	white blood cell
WOCBP	women of childbearing potential

#### 3. SYNOPSIS

#### **Protocol Number:**

APL2-201

#### **Protocol Title:**

A Phase 2 Study to Evaluate the Safety and Biologic Activity of Pegcetacoplan in Patients With IgA Nephropathy, Lupus Nephritis, Primary Membranous Nephropathy, or C3 Glomerulopathy (C3 Glomerulonephritis and Dense Deposit Disease)

#### **Version Number:**

Amendment 7

## **Investigational Product, Dose, and Route of Administration:**

- 1. Pegcetacoplan (APL-2)
- 2. 360 mg daily; may transition to 1080 mg twice weekly
- 3. Subcutaneous infusion

## **Study Phase and Type:**

Phase 2 study consisting of an open-label, nonrandomized group of patients with complement-mediated nephropathies.

## **Number of Planned Subjects:**

Up to approximately 48 patients (pegcetacoplan treatment naive) with clinical diagnosis (confirmed by renal biopsy) of IgA nephropathy (IgAN), lupus nephritis (LN), primary membranous nephropathy (primary MN), or C3 glomerulopathy (C3G), with 6-12 patients per disease.

## **Treatment Groups:**

1. Pegcetacoplan in patients with IgAN, LN, primary MN, or C3G

## **Duration of Study Participation:**

The planned length of participation in the study for each subject is 76 weeks, including an approximate 4-week screening period, 48-week treatment period and 24-week follow-up period (Part A, Core Study Phase). Any subject who, in the opinion of the investigator, is experiencing clinical benefit from pegcetacoplan administration will be invited to participate in Part B, a Long-Term Extension Phase in order to continue to receive treatment with pegcetacoplan until it is commercially available for the disease under treatment. If invited to participate in Part B, the subject can enter the Long-Term Extension Phase as soon as they complete the 48-week treatment period and do not need to participate in the 24-week follow-up period.

## **Study Population:**

Patients, at least 18 years of age with either IgAN, LN, primary MN, or patients at least 16 years of age with C3G.

### **Rationale for the Study:**

The 4 diseases of IgAN, LN, primary membranous nephropathy (primary MN) and C3 glomerulopathy (C3G) have a shared pathogenesis of activation of the central complement component, C3. These diseases all involve activation of either 2 or 3 of the pathways to C3 activation (classical, lectin, or alternative complement activation). Complement activation in glomeruli induces the inflammatory cascade, which results in renal injury and loss of function. Both decreased circulating C3 levels and mesangial C3 deposition are independently associated with poor renal outcome in patients with complement-mediated glomerulopathies, which suggests that systemic and local activation of complement play a role in the disease progression. Genetic mutation also supports the importance of the complement alternative pathway in complement-mediated glomerulopathies. By targeting therapy directly to the key junction of the classical, lectin, and alternative complement activation pathways, pegcetacoplan documented C3 inhibitory activity may control the C3-mediated inflammatory response and the downstream inflammatory events responsible for the renal manifestations of injury common to all these diseases. To date, no safety signals have emerged from ongoing studies in paroxysmal nocturnal hemoglobinuria (PNH) or age-related macular degeneration that preclude further development with pegcetacoplan in other indications. Thus, this proposed Phase 2 study's aim is to explore treatment efficacy and safety of pegcetacoplan for the treatment of IgAN, LN, primary MN, and C3G.

## **Study Objectives and Endpoints:**

## **Objectives**

The primary objectives of this study are to establish preliminary efficacy and safety of pegcetacoplan in patients with IgAN, LN, primary MN, and C3G.

## **Endpoints**

Primary efficacy endpoint:

• Proteinuria reduction from baseline to Week 48, based on urinary protein-to-creatinine ratio (uPCR)

Secondary efficacy endpoints:

- All disease groups: changes of disease-specific biomarkers:
  - Serum C3 levels
  - AH50 and C3a concentrations
  - Serum albumin levels
- All disease groups: complete clinical remission defined as normalization of proteinuria as defined by <200 mg/g uPCR at Week 48
- All disease groups: stabilization or improvement in estimated glomerular filtration rate (eGFR) from baseline to Week 48

#### Exploratory endpoints:

• Complete renal response: defined as <200 mg/g uPCR and stabilization or improvement in eGFR from baseline to Week 48

- Changes of disease-specific biomarkers:
  - LN: autoantibodies to double-stranded DNA, C3, and C1q
  - Primary MN: autoantibodies to phospholipase A2 receptors (PLA2R)
  - C3G: C3 nephritic factor (Part A only)

## Pharmacokinetic endpoint:

• Pegcetacoplan pharmacokinetic concentrations

## Pharmacodynamic endpoints:

- Pegcetacoplan activity: Absolute levels, change from baseline, and % change from baseline in CH50, C3, C3a, C4, C5a, and soluble C5b9 complex (sC5b9)
- Immunogenicity: Presence of autoantibodies to polyethylene glycol and pegcetacoplan throughout treatment and follow-up periods

## Safety endpoints:

- Physical examination; incidence and severity of adverse events (AEs)
- Changes from baseline in laboratory parameters
- Changes from baseline in electrocardiogram parameters

## **Study Design:**

This is a prospective Phase 2 study, consisting of a single cohort with a total of approximately 48 patients among the 4 indications. This is an open-label study, with 48 patients clinically diagnosed with IgAN, LN, primary MN, or C3G (with 6-12 patients per disease). Each clinical diagnosis must be confirmed by renal biopsy prior to dosing with pegcetacoplan. Subject participation will include a Part A Core Study Phase that consists of an approximate 4-week screening period, 48-week treatment period, and 24-week safety follow-up. During the treatment period, patients will receive subcutaneous (SC) once daily infusions of 360 mg pegcetacoplan. Following the completion of 48-week treatment period in Part A Core Study Phase, if invited, subjects may participate in Part B, the Long-Term Extension Phase, in order to continue to receive treatment with pegcetacoplan until it is commercially available for the disease under treatment. If they are invited to participate in Part B, they do not need to complete the 24-week follow-up period.

For each indication, patients whose underlying renal disease is stable for at least 2 months prior to the first dose may enter the study. In this trial, stable renal disease should include stable eGFR, proteinuria, and blood pressure, as well as a stable and optimized treatment regimen for their renal disease, in the opinion of the primary investigator (PI) (see Section 10.1 for the complete detailed eligibility information). Upon completion of the screening period, patients who meet all of the inclusion and none of the exclusion criteria will begin the treatment phase of the study. The treatment phase will consist of once daily, self-administered, SC dosing of 360 mg pegcetacoplan at home, with the exception of all scheduled clinic visits. During scheduled Visit 4 only, the site staff will assist in administering the first SC dose of pegcetacoplan. At Visits 5-

15 subjects will self-administer pegcetacoplan in the presence of the site staff and undergo various safety and efficacy assessments by qualified site staff. Subjects may be switched over to twice-weekly dosing as early as Week 24. Any subject who is invited to participate in Part B who has not already switched over to twice-weekly dosing, must do so at the beginning of Part B. If a subject transitions to the twice-weekly dosing, they need to follow the dose transition visits (T1, T2, and T3) as outlined in Section 10.1, Table 2 (during Part A) or Appendix 1, Table A1 (for Part B). The change in proteinuria from baseline through the end of treatment will be assessed as the primary endpoint. Urinary protein-to-creatinine ratio (PCR) will be used to measure changes in proteinuria for the primary endpoint.

After completion of the 48-week treatment period, each subject will have the opportunity to enter Part B, the Long-Term Extension Phase (see Appendix 1), at the discretion of the investigator. If the subject does not enter Part B, he or she will enter into a 24 week follow-up period, consisting of 6 clinic visits at weeks 50, 52, 54, 60, 66, and 72 (Exit Visit). Various safety assessments will be undertaken during these clinic visits, and follow-up phone calls will be performed to gain relevant safety information. Patients will be maintained on their baseline treatment regimen during treatment and the follow-up period, as determined by the PI in consultation with the medical monitor. During the study, changes to the baseline treatment regimen should be avoided to the extent possible and made only when required for the well-being of the patient, in the opinion of the PI.

Safety summaries will be presented over the screening period, 48 weeks of treatment and 24 weeks of follow-up, as well as the overall duration of the study.

An external, independent safety monitoring committee will assess the safety/tolerability data of the study.

Subject level discontinuation will occur for any subject who develops a serious adverse event (SAE) due to infection confirmed to be caused by encapsulated organisms (see Section 8.3 for further information) or any subject with a sustained and significant reduction in renal function, as defined by one of the following: initiation of chronic dialysis, a confirmed and sustained eGFR ≤15 mL/min/1.73 m² or a confirmed and sustained reduction in eGFR of at least 30% which is drug related in the opinion of the PI. A reduction in eGFR would be considered confirmed if present on 2 separate consecutive measurements and considered sustained if the 2 measurements are at least 1 week apart. Subject level discontinuation can also occur for any individual for whom the PI deems it in the best interest of the patient to not continue in the study. Indication level discontinuation will occur if 2 or more subjects in a particular indication are discontinued by these criteria.

Subjects who do not meet the criteria for participation in the study (screen failure) may be rescreened. The timeframe and scope of eligibility reassessment will be determined by the sponsor. Any requests to rescreen an individual more than one time must be approved by the sponsor. For each rescreening, the individual must sign a new informed consent form and will be assigned a new identification number. Record of the subject's prior identification number and screening should be maintained with the source documents. Subjects who received vaccinations per protocol within 2 years of their rescreening date do not need to have the respective vaccination repeated but may do so at the discretion of the investigator.

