After completion of the 48-week treatment period, any subject who, in the opinion of the investigator, is experiencing clinical benefit from pegcetacoplan treatment, will be invited to participate in Part B, the Long-Term Extension Phase (see Appendix 1 [Section A1.1]). If the subject does not enter Part B, he or she will enter the 24-week follow-up period, consisting of 6 clinic visits at weeks 50, 52, 54, 60, 66, and 72 (Exit Visit). Various safety assessments will be undertaken during this visit clinics. Patients will be maintained on the standard of care during treatment and the follow-up period, as determined by the PI in consultation with the medical monitor.

An external, independent safety monitoring committee (SMC) will assess the progress and cumulative safety/tolerability data of the study at specified times described in Section 13.4.3.

Any subject with a sustained and significant reduction in renal function, as defined by one of the following: initiation of chronic dialysis, a confirmed and sustained eGFR ≤15 mL/min/1.73 m^2 or a confirmed and sustained reduction in eGFR of at least 30% which is drug related in the opinion in the PI. A reduction in eGFR would be considered confirmed if present on 2 separate consecutive measurements and sustained if the 2 measurements are at least 1 week or apart. Subject level discontinuation can also occur for any individual for whom the PI deems it in the best interest of the patient to not continue in the study. Indication level discontinuation will occur if 2 or more subjects in a particular indication are discontinued by these criteria.

Subjects who do not meet the criteria for participation in the study (screen failure) may be rescreened. The timeframe and scope of eligibility reassessment will be determined by the sponsor. Any requests to rescreen an individual more than one time must be approved by the sponsor. For each rescreening, the individual must sign a new informed consent form and will be assigned a new identification number. Record of the subject's prior identification number and screening should be maintained with the source documents. Subjects who received vaccinations per protocol within 2 years of their rescreening date do not need to have the respective vaccination repeated but may do so at the discretion of the investigator.

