### 13.5. Treatment Discontinuation and Study Withdrawal

Subjects will be considered to have completed the study when they have completed the Week 72 exit visit activities described in the Schedule of Assessments in Section 4, when they have enrolled in a subsequent study of pegcetacoplan, or when they have discontinued study treatment and completed any early termination activities.

A subject may withdraw from the study at any time, for any reason, without prejudice to his/her future medical care by the physician or at the institution. If a subject discontinues or is withdrawn from study treatment for any reason, the study site must immediately notify the medical monitor.

Treatment may be discontinued and/or a subject's participation in the study may be discontinued, for any of the following reasons:

- 1. Any serious adverse event (SAE), clinically significant AE, severe laboratory abnormality, intercurrent illness, or other medical condition (including infections) that indicates to the PI that continued participation is not in the best interest of the subject.
- 2. Subject's decision to withdraw.
- 3. Subject's failure to comply with protocol requirements (including pregnancy) or study-related procedures.
- 4. Termination of the study by the sponsor, US Food and Drug Administration, or other regulatory authorities.
- 5. Liver Toxicity (please refer to Section 13.5.1 for further details).
- 6. Sustained and significant reduction in renal function (see more details below).

A sustained and significant reduction in renal function is defined by one of the following: initiation of chronic dialysis, a confirmed and sustained eGFR ≤15 mL/min/1.73 m² or a confirmed and sustained reduction in eGFR of at least 30% which is drug related in the opinion in the PI. A reduction in eGFR would be considered confirmed if present on 2 separate consecutive measurements and sustained if the 2 measurements are at least 1 week or apart.

The reason for treatment discontinuation and/or withdrawal from the study must be recorded in the subject's source document.

Subjects who discontinue study treatment prior to the end of the treatment period, should undergo all follow-up visits and procedures through study completion (Exit Visit), unless unwilling or unable, or consent has been withdrawn. Subjects who wish to fully withdraw from the study before Visit 15, should be encouraged to complete the Early Termination Exit Visit.

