After completion of the 48-week treatment period, each subject will have the opportunity to enter Part B, the Long-Term Extension Phase, at the discretion of the investigator. If the subject does not enter Part B, he or she will enter a 24 week follow up period, consisting of 6 clinic visits at weeks 50, 52, 54, 60, 66, and 72 (Exit Visit). Various safety assessments will be undertaken during these clinic visits, and follow-up phone calls will be performed to gain relevant safety information. Patients will be maintained on their baseline treatment regimen during treatment and the follow-up period, as determined by the Principal Investigator (PI) in consultation with the medical monitor. During the study, changes to the baseline treatment regimen should be avoided to the extent possible and made only when required for the well-being of the patient, in the opinion of the PI.

Safety summaries will be presented over the screening period, 48 weeks of treatment and 24 weeks of follow-up, as well as the overall duration of the study.

An external, independent Safety Monitoring Committee (SMC) will assess the safety or tolerability data of the study.

Subject level discontinuation will occur for any subject who develops SAE due to infection confirmed to be caused by encapsulated organisms (see Protocol Section 8.3 for further information) or any subject with a sustained and significant reduction in renal function, as defined by one of the following: initiation of chronic dialysis, a confirmed and sustained eGFR \leq 15 mL/min/1.73 m2 or a confirmed and sustained reduction in eGFR of at least 30% which is drug-related in the opinion in the PI. A reduction in eGFR would be considered confirmed if present on two separate consecutive measurements and sustained if the two measurements are at least 1 week or apart. Subject level discontinuation can also occur for any individual for whom the PI deems it in the best interest of the patient to not continue in the study. Disease Group level discontinuation will occur if two or more subjects in a particular disease group are discontinued by these criteria.

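### The mandatory stop for a serious encapsulated-organism infection in the Synopsis and SAP 3.1 has dropped out of Protocol Section 10, and no other body section restores it

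*Protocol*

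**What the plan says.** **Protocol Synopsis, Study Design.** The rule is mandatory: "Subject level discontinuation will occur for any subject who develops a serious adverse event (SAE) due to infection confirmed to be caused by encapsulated organisms". The same sentence adds sustained and significant renal decline. An investigator best-interest clause follows, and then the consequence for the disease group: "Indication level discontinuation will occur if 2 or more subjects in a particular indication are discontinued by these criteria".

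**SAP 3.1.** The same structure: "Subject level discontinuation will occur for any subject who develops SAE due to infection confirmed to be caused by encapsulated organisms", and then "Disease Group level discontinuation will occur if two or more subjects in a particular disease group are discontinued by these criteria".

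**Protocol Section 10.** The corresponding paragraph begins "Any subject with a sustained and significant reduction in renal function, as defined by one of the following: initiation of chronic dialysis" and continues through the eGFR thresholds without ever saying what happens to that subject. The best-interest clause and the two-subject indication rule follow, as in the Synopsis. Infection is not mentioned.

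**Protocol Section 13.5.** The list of reasons is introduced by "Treatment may be discontinued and/or a subject's participation in the study may be discontinued, for any of the following reasons". Item 1 covers serious adverse events and, among other things, any "or other medical condition (including infections) that indicates to the PI that continued participation is not in the best interest of the subject". Item 5 is liver toxicity and item 6 is renal decline. The section defines renal decline but does not say that it compels a stop, and it states no indication-level rule.

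**Protocol Section 13.5.1.** For liver toxicity, by contrast, stated laboratory thresholds require immediate discontinuation.

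**The concern.** Stopping rules are useful only if every place a site consults leads to the same action. Here the Synopsis and the SAP compel a stop, the study design section does not mention the criterion, and the withdrawal section leaves it to judgement. A site working from the body of the protocol could continue dosing a subject whom the Synopsis says must stop.

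The consequence goes beyond that subject. The indication rule counts subjects discontinued under the listed criteria, so its reach depends on which list is read.

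The protocol itself identifies infection with encapsulated organisms as a potential risk of complement inhibition (Sections 7.3 and 8.3). The wording also matters for any subject still treated in Part B. Appendix 1 (A1.1) refers readers to the body of the main protocol for anything it does not describe. Scheduled safety committee meetings run only until all subjects have completed Week 48 (Section 13.4.3, which allows ad hoc reviews at any time), and SAP Section 12 plans no committee for Part B.

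**Working it through.** The plan gives no figure on this point and no arithmetic applies. The check compares the texts.

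| Place | Infection SAE | Renal decline | Indication rule |
|---|---|---|---|
| Synopsis | mandatory | mandatory | stated; covers infection |
| SAP 3.1 | mandatory | mandatory | stated; covers infection |
| Section 10 | not listed; only through the best-interest clause | listed, but no main verb | stated; infection counts only if the investigator stops the subject |
| Section 13.5 | possible reason, on investigator judgement | possible reason | not stated |

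**Step 1: lost text or deliberate change?** The renal sentence in Section 10 has a subject and a definition but no predicate. The next sentence on discontinuation says that it can *also* occur on best-interest grounds, which presupposes an earlier statement that is no longer there. Restoring the Synopsis opening repairs both faults. The Amendment 7 summary of changes records no removal of the infection rule. SAP 2.0, written to Amendment 7, still carries it. All this points to a dropped clause.

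**Step 2: does another body section supply the rule?** Section 8.3, to which the Synopsis refers, names the organisms and provides for vaccination, monitoring and prompt contact with the investigator. Section 12.6.1 provides for antibiotics. Neither says that dosing must stop. Section 13.5 mentions infections in item 1 without naming encapsulated organisms and without an obligation.

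**Step 3: follow one case through each text.** Suppose two subjects with the same disease each have an SAE from a confirmed encapsulated-organism infection, and neither meets a renal criterion.

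- Synopsis and SAP 3.1: both must stop, the count reaches two, and the indication stops.
- Section 10: each stops only if the investigator judges that to be in the subject's interest. The indication stops only if that judgement is made in both cases.
- Section 13.5: each may be stopped, and nothing there links the decision to the indication.

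The same events therefore compel an indication stop on one reading and not on another.

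**Step 4: compare with liver toxicity.** It appears in the same Section 13.5 list as infection and renal decline, but a subsection makes it mandatory. The other two have no equivalent body text, since the Section 10 renal sentence is incomplete.

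**The case against.** The strongest reply is that nothing conflicts. The Synopsis is part of the protocol and applies to every subject. The permissive verb in Section 13.5 heads a general list that also holds the subject's own decision to withdraw, regulatory termination and the liver criterion that Section 13.5.1 makes mandatory, so it need not mean optional. A site that stops an infected subject complies with every section. Section 10 keeps the best-interest clause immediately before the indication rule, so an infected subject stopped by the investigator can still count. Every SAE must reach the sponsor within 24 hours (Section 15.2), so such a case would not go unnoticed.

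Most of this stands, and it rules out several stronger readings that a reader might infer:

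- *The protocol has no mandatory infection stop.* It has one, in the Synopsis.
- *Section 13.5 contradicts the Synopsis.* It is less specific, not contrary.
- *Under Section 10 an infection can never count toward the indication rule.* It can, if the investigator stops the subject.
- *Part B subjects are being dosed under the defective text now.* The documents do not establish this. SAP Section 1 describes SAP 2.0 as covering the final analysis of subjects who rolled over, and no count of subjects on treatment is given.
- *A probability can be put on the harm.* The documents give no event rate, and Section 7.3 reports no serious encapsulated-bacteria infections to date.

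The reply does not remove the gap. Prompt reporting tells the sponsor about the event but does not oblige anyone to stop dosing. An investigator who reads Sections 10 and 13.5 and judges that treatment should continue would find nothing there to the contrary.

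**Conclusion.** The point holds as an internal inconsistency in a safety stopping rule. Section 10 has lost the clause that makes the infection SAE a mandatory stop and gives the renal criteria their verb. Section 13.5 does not make up for the loss. The practical exposure is narrow: an investigator who sees a qualifying infection, chooses to continue, and does not apply the Synopsis. Its effect extends to the indication-level rule, because there the count depends on that choice.

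The size is textual only; no event rate or level of risk is claimed. The conclusion rests on two assumptions: that sites consult the body sections for discontinuation decisions, and that the Synopsis and SAP 3.1 express the intended rule, which the broken sentence in Section 10 supports. It matters in practice for any subject still being dosed, including in Part B, and that number is not known from the documents.

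**What to change.** 1. **Section 10.** Put the Synopsis opening back before the renal text: "Subject level discontinuation will occur for any subject who develops a serious adverse event (SAE) due to infection confirmed to be caused by encapsulated organisms", followed by the Synopsis's cross-reference to Section 8.3 and the word *or*, and then the existing renal sentence from *any subject* onward.
2. **Section 13.5.** Add one sentence: *Discontinuation is mandatory for the infection and renal criteria in Section 10, and these subjects count toward the indication-level rule there.*

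Leave the existing follow-up provisions as they are: the early-discontinuation visits in Section 13.4, the exception in Section 13.5 for subjects who are unwilling, unable or have withdrawn consent, and the Part B early-termination visits in A1.1.2. The added sentence deliberately does not redefine whether subject-level discontinuation means stopping treatment or leaving the study. If the sponsor wants to settle that, it should do so openly as a separate change.

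The Synopsis and SAP 3.1 need no change for this point. The cost is a short amendment with sponsor agreement and IRB/IEC approval (Section 17.5). Re-consent is needed only if the change may directly affect a subject's decision to continue (Section 17.3.3). Endpoints, data collection and analyses are unaffected.
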